4.5. Subject Replacement

Participant who withdraws from the study post-randomisation will not be replaced.

4.6. Subject and Study Completion

A completed subject is one who has completed all phases of the study including the follow-up visit.

The end of the study is defined as the date of the last subject’s last visit.

5. PRODUCT INFORMATION

5.1. Study Product

The following study product will be supplied by the Clinical Supplies Department, GSKCH:

	Test Product
Product Name	Fortified malt based food
Product Formulation Code	CCI [REDACTED]
Dose	27 grams
Route of Administration	Oral
Dosing Instructions	27 grams powder made up in 150 mL lukewarm water, administered twice daily

Other items to be supplied by the Clinical Supplies Department, GSKCH:

Name of Item	Purpose
Tumblers	To assist with the addition of the correct volume of lukewarm water during the

 GlaxoSmithKline	Document Name	Clinical Study Protocol 204477		
	Type	Version	Document Identifier	Effective Date
	eldo_clinical_doc	5.0; Most-Recent; Effective; CURRENT	090032d580daa95e	10-Oct-2017 06:16:49
	Reason For Issue	Auto Issue		

	preparation of daily test dose and to assist with the assessment of compliance (volume remaining)
Stirrers	To assist mixing during the preparation of daily test dose

5.2. Dose Schedule

Participants will be administered two doses of the drink (approx 150 mL each) daily for 9 months. To maximise the interval between the two doses, during all school days study staff will make efforts to administer one dose as soon as the participants enter the school and the second dose will be provided just prior to school dismissal. At home, each day one dose will be administered preferably in the morning and the second dose will be administered preferably in evening, by parents/LARs.

5.3. Dose Administration

The graduated tumbler will be filled with luke-warm water up to the 150 mL mark. The entire contents of one sachet will be gradually emptied in the water filled tumbler with intermittent stirring to avoid formation of lumps. The reconstituted test product will be provided to the participants immediately for oral consumption.

On all school days, two test product doses (each dose of 27g in 150mL lukewarm water) will be provided to the participants at schools, under the supervision of trained research personnel. At schools, the test product will be reconstituted by site staff using bottled water. The participants will be given counted number of single serve sachets (27grams each) for consumption over weekends and during other school holidays and school absenteeism. The participant's parents/LARs will be informed during the consenting process on how to prepare the product in lukewarm water (boiled water will be recommended).

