3. STUDY PLAN

3.1. Study Design

Overall Design
This is a single centre, multiple sites, open label, two-arm, parallel-group, stratified by gender, matched pair cluster randomised, controlled study.
Visit 1 - Screening Visit

The following assessments will be conducted in the order written:
 
 • Informed consent and assent • Demographics • Medical history • Current/concomitant medications • General physical examination • Vital signs • Hb assessment using Pronto • Anthropometric measurements (height and weight) • Inclusion/exclusion criteria evaluation • Subject Eligibility • 24 hr dietary recall & dietary diversity survey • Parental/LAR training on the completion of the ‘Symptom Check List’

	Document Name	Clinical Study Protocol 204477		
	Type	Version	Document Identifier	Effective Date
	eldo_clinical_doc	5.0; Most-Recent; Effective; CURRENT	090032d580daa95e	10-Oct-2017 06:16:49
	Reason For Issue	Auto Issue		

- Dispense blank Parent/LAR Symptom Checklist and Product Compliance Report Forms

Visit 2 - Baseline Visit

The following assessments will be conducted ~~in the order written:~~

- Current/concomitant medications
- Continued eligibility criteria
- Sample collection for urinary Neopterin test & lactulose/mannitol test
- Sample collection for analysis of serum ferritin, sTfR, CRP, AGP, sIgA & nutritional biochemistry (for micronutrients vitamins A, B6, B12, ~~C~~, D, E, folate, and of the trace elements selenium, zinc, copper, and iron)
- AE monitoring

Visit 3, 4, 5, 6, 7, 8, 9, SPWR and Product Administration Visits

The following assessments will be conducted:

- Current/concomitant medications
- Continued eligibility criteria
- Dietary counselling will be administered to all study participants and their parents/LARs.
- Test product will be administered to all study participants in the test group.
- SPWR visits will be conducted on a weekly basis until End of Study Visit. Parent/LAR symptom checklist & Product Compliance Report Forms will be collected and reviewed.
- AE monitoring

Visit 10 - End of Study Visit

The following assessments will be conducted ~~in the order written:~~

- Current/concomitant medication

	Document Name	Clinical Study Protocol 204477		
	Type	Version	Document Identifier	Effective Date
	eldo_clinical_doc	5.0; Most-Recent; Effective; CURRENT	090032d580daa95e	10-Oct-2017 06:16:49
	Reason For Issue	Auto Issue		

- General physical examination
- Vital signs

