5.5. Product Compliance

For doses administered at school, study-personnel will supervise and ensure complete consumption of test products. Random home visits will be made by site staff to ensure compliance of product consumption at home. Details of daily product consumption (including weekends, school holidays and school absenteeism) will be entered in the CRF.

In the unlikely event that the test product is incompletely consumed (due to accidental spillage, for instance) or not administered, this will also be noted in the CRF along with the product volume that was not consumed (in case of incomplete consumption). In case this happens at home, parents/LAR will need to enter details in the Product Compliance Report (Appendix 4). Site staff will dispense as many blank reports as appropriate for recording details. Each report will be numbered in an ascending order (for each participant) and records should be maintained to track the total number of reports dispensed and collected. Participant will be considered as non-compliant if the participant consumes less than 70% of the total amount of recommended (for the entire study duration) dose.

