Other morbidity outcomes such as number of illness days, number of episodes, frequency due to GI and respiratory illnesses, as defined in the study protocol, will be calculated programmatically using statistical analysis software (SAS).

Data on diagnosis and morbidity outcomes by study physician on the DF will be used for analysis. DF will be filled as per the details obtained from:

- Symptom checklist filled by parents/LARs
- External clinical record, if treated by an external physician
- Direct information by participants/parents/LARs
- Clinical history and examination by study physician

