6.12.1. Collection of Symptom Checklist

Parent/LAR-reported symptom checklist will be collected on each weekly review. Physician will review the parent/LAR Symptom checklist and conduct clinical examination of only those participants who present with symptoms on the symptom checklist or inform the physician directly.

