6.12.2. Study Physician Clinical History and Examination

Study physician will be made available at school on all school days during school timings.

When the participant **falls sick at school** during school timings with the pre-specified symptoms related to GI and respiratory illnesses, participant will be presented to the study physician. Study physician will collect relevant clinical history from participants and parents/LARs (if available). Study physician will systematically evaluate the symptoms using well-defined, pre-established criteria and will make objective diagnosis of the clinical outcomes, as defined in the study protocol.

When study participant **fall sick but are not at school** (e.g. during holidays, after school dismissal etc), with the pre-specified symptoms related to GI and respiratory illnesses, parents/LARs would need to complete the 'symptom checklist' provided to them. Symptom checklist would be presented to study physician by the participants/parents/ LARs. In case, if an external physician is consulted for the treatment, clinical record form from the same would also be presented to the study physician along with symptom checklist. Study physician will collect relevant clinical history from participants and parents/LARs (if available). Study physician will evaluate and verify parent reported data on symptom checklist and clinical record form from external

 GlaxoSmithKline	Document Name	Clinical Study Protocol 204477		
	Type	Version	Document Identifier	Effective Date
	eldo_clinical_doc	5.0; Most-Recent; Effective; CURRENT	090032d580daa95e	10-Oct-2017 06:16:49
	Reason For Issue	Auto Issue		

physician. Study physician will systematically evaluate the symptoms (if still present in the participants) using well-defined, pre-established criteria and will make objective diagnosis of the clinical outcomes, as defined in the study protocol.

Diagnosis by study physician on DF will be used for analysis. In case of a conflict between parent-reported symptoms, external physician's reported diagnosis and study physician's diagnosis, the study physician's diagnosis will supersede.

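### The test arm has an extra staff-mediated route by which illness can reach the open-label primary endpoint, and no planned analysis addresses it

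*Protocol*

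**What the plan says.** **Common to both arms.** Under Protocol 6.11.3, parents mark every listed symptom for every day, including symptom-free days. Under 6.12, the study physician reviews all participants' checklists weekly, with telephone or home follow-up when a review is missed. Section 6.12.2 adds "Study physician will be made available at school on all school days during school timings", and children who fall sick there are brought to that physician.

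**Test arm only.** Section 5.3 provides "On all school days, two test product doses", which "will be provided to the participants at schools, under the supervision of trained research personnel". Section 5.2 asks staff to try to "administer one dose as soon as the participants enter the school and the second dose will be provided just prior to school dismissal". Section 5.5 adds "Random home visits will be made by site staff to ensure compliance of product consumption at home". Controls receive no product and have no matching contact.

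**How contact can reach the endpoint.** Section 3.1 lists adverse-event monitoring under the heading "Visit 3, 4, 5, 6, 7, 8, 9, SPWR and Product Administration Visits", and SAP 1.1 does the same. Section 7.4 obliges the investigator or designee to ask at each visit whether the child has felt unwell or had symptoms; one of the optional time frames in that question is since the last dose. Under 6.12.1 the physician will "conduct clinical examination of only those participants who present with symptoms on the symptom checklist or inform the physician directly". Section 6.11.3 names "Direct information by participants/parents/LARs" among the sources of the Diagnosis Form, and Appendix 5 gives each occurrence an adverse-event report number.

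**Who decides.** The trial is open label for site, sponsor and CRO (5.9.2). The study physician's diagnosis prevails over the parent's report and any external diagnosis (6.12.2), and that physician judges whether the cause is non-infectious (6.11.1). No blinded adjudication is described. The one supportive analysis, the MMRM in SAP 4.4.1.3, does not bear on ascertainment.

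**The concern.** The case definition has a low threshold: under Protocol 6.11.1 a single acute symptom such as sneezing or a runny nose qualifies as respiratory illness. Whether such a symptom is counted depends on somebody mentioning it. Test children have two staff contacts on every school day at which it could be mentioned and, on a literal reading of 3.1 with 7.4, at which it must be asked about. Controls have no equivalent.

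The plan matches dietary counselling between arms for quality, content and duration (sections 1 and 3.4), so it treats equal handling as important. It does not extend that to staff contact.

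Extra questioning could raise recorded ill days in the test arm and mask a benefit. Unblinded parents or physicians who expect the product to work could lower them and create one. Because success is defined as a significant decrease (9.2.3), the second possibility bears directly on a false claim.

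**Working it through.** **1. The plan's own figure (Protocol 9.1, SAP 1.4).** Inputs: means 7.0 and 6.3, SDs 2.65 and 2.51, two-sided 5%, 80% power, design effect 1.5, 30% dropout.

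- Pooled SD = √((2.65² + 2.51²)/2) = 2.581.
- The normal formula gives n = 214 per arm; the t-test gives 215 (power 80.1%).
- 215 × 1.5 = 322.5, rounded to 323 per arm, 646 in total.
- 323/0.70 = 461.4, rounded to 462 per arm, 924 in total.

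The stated sizes reproduce.

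**2. Contact count.** Nine months is 9 × 365.25/12/7 ≈ 39 weeks, so about 39 weekly reviews in each arm. The documents do not give the number of school days. Assuming 150 to 200, the test arm adds 300 to 400 supervised-dose contacts per child.

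**3. Effect of unequal capture.** Let r be the completeness of recording in the test arm relative to control. No value is given in the documents, so a range is shown. With variance equal to the mean, as the plan assumes:

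- recorded test mean m = r × true test mean
- effective n per arm = 323/1.5 = 215.3
- SE = √((7 + m)/215.3)
- P(significant, favouring test) = Φ((7 − m)/SE − 1.96)

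Example, true mean 6.3 and r = 1.05: m = 6.615, difference 0.385, SE = √(13.615/215.3) = 0.251, Φ(1.53 − 1.96) = 33%.

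True 10% reduction:

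| r | Recorded difference (days) | Power |
|---|---|---|
| 0.95 | 1.02 | 98.5% |
| 1.00 | 0.70 | 80% |
| 1.03 | 0.51 | 53% |
| 1.05 | 0.39 | 33% |
| 1.08 | 0.20 | 12% |
| 1.11 (= 7/6.3) | 0 | 2.5% |

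No true effect (true mean 7.0 in both arms):

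| r | P(significant, favouring test) | P(significant, against test) |
|---|---|---|
| 0.90 | 80% | 0% |
| 0.95 | 28% | 0% |
| 1.00 | 2.5% | 2.5% |
| 1.05 | 0% | 27% |
| 1.10 | 0% | 76% |

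**4. What could be untangled afterwards.** Appendix 5 asks once per week whether a checklist was received and whether the child reported directly. Each occurrence carries dates but no source. Appendix 3 is dated by symptom and day, so matching by date would show which occurrences have checklist support. It would not show how an occurrence first came to light.

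**5. Physician, only if each school keeps its own.** Suppose acceptance of ill days varies between physicians with coefficient of variation c (assumed). With two schools per arm (SAP 3.3) and an average mean of 6.65, the added SE of the difference is √(2 × (6.65c)²/2) = 6.65c. That is 0.13 days at c = 2% and 0.33 at c = 5%. The planned SE is √(2 × 6.66/215) = 0.249.

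**The case against.** The best defence is that the formal process is identical. Daily checklist, weekly review and on-site physician apply to every child, and a missed review triggers follow-up. That stands, and it limits how much illness the extra contact could add. It does not make the extra contact equal.

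Four stronger readings are tempting, and the documents do not support them:

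- **That controls are seen only weekly.** This is true of scheduled review alone. A physician is at school every school day in both arms.
- **That there is one physician per school.** Section 6.12.2 requires presence, not fixed assignment. A rotating rota fits the text equally well, so step 5 is conditional. If assignment is fixed, physician variation forms part of the between-school variance, which the design effect is meant to cover and which the random school effect in SAP 4.4.1.2 models.
- **That illness is unequally captured, to the product's disadvantage.** Unequal capture is a risk inferred from the design. Its direction is undetermined, because extra contact and unblinded judgement can pull opposite ways.
- **That the extra cases can never be separated.** Date matching would recover part of the information.

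It is also fair to say that section 3.1 may use the word visits loosely and that staff may never ask the question at dosing. That is a reason to settle the text.

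**Conclusion.** The point holds as a design risk of moderate weight that should be fixed. The text allows, and on a literal reading requires, more frequent symptom questioning in the test arm. The answers can enter the form that defines the primary endpoint, the deciding physician is unblinded, and no planned analysis tests the consequence.

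The size depends on an assumed capture ratio. A relative difference of 5% to 11% is enough to cut power from 80% to about 33% or to cancel the 0.7-day difference. Under-capture of 5% with no true effect raises the chance of a false claim for the product from 2.5% to about 28%. These figures rest on the plan's Poisson variance and its design effect of 1.5, and they show sensitivity only. Nothing in the documents indicates which ratio would occur or on which side of 1 it would fall.

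**What to change.** (a) In Protocol 3.1 and 7.4, state that dose-administration and compliance contacts are not visits for the purpose of the symptom question. Ask that question on the same schedule in both arms, for example at the weekly physician review. Spontaneous reports are still recorded whenever they arise. An instruction to product staff that left the adverse-event question in place at dosing would miss the main documented route.

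(b) Add to each occurrence on Appendix 5 how it first came to light (parent checklist, presented at school or told to study staff, external record), and an analysable physician identifier. The form's completed-by line is not enough for analysis.

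(c) Pre-specify in the SAP a sensitivity analysis that repeats the primary model on ill days from occurrences supported by the parent checklist. First reconcile Appendix 3 with 6.11.1: as printed, the checklist has no row for stuffy or blocked nose, which is a case-defining symptom. State that parents are unblinded too, so this analysis equalises procedure and not expectation. If forms have already been collected, matching Appendix 3 to Appendix 5 by date is the fallback.

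(d) If physicians are assigned to fixed schools, rotate the existing physicians within each matched pair on a fixed calendar.

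Cost: a clarification of the protocol text, two fields on a form, one repeated model and, if needed, a rota. No extra staff are required. The drawback is some loss of continuity between a school and its physician.

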5.4. Dose Modification

No modification to the dosing regimen will be allowed. Any variation from the dosing regimen will be reported to the study site personnel and details will be entered on the test product administration log and then entered into the CRF.

 GlaxoSmithKline	Document Name	Clinical Study Protocol 204477		
	Type	Version	Document Identifier	Effective Date
	eldo_clinical_doc	5.0; Most-Recent; Effective; CURRENT	090032d580daa95e	10-Oct-2017 06:16:49
	Reason For Issue	Auto Issue		

5.5. Product Compliance

For doses administered at school, study-personnel will supervise and ensure complete consumption of test products. Random home visits will be made by site staff to ensure compliance of product consumption at home. Details of daily product consumption (including weekends, school holidays and school absenteeism) will be entered in the CRF.

In the unlikely event that the test product is incompletely consumed (due to accidental spillage, for instance) or not administered, this will also be noted in the CRF along with the product volume that was not consumed (in case of incomplete consumption). In case this happens at home, parents/LAR will need to enter details in the Product Compliance Report (Appendix 4). Site staff will dispense as many blank reports as appropriate for recording details. Each report will be numbered in an ascending order (for each participant) and records should be maintained to track the total number of reports dispensed and collected. Participant will be considered as non-compliant if the participant consumes less than 70% of the total amount of recommended (for the entire study duration) dose.

5.6. Precautions

No special precautions are necessary provided the test product is used in accordance with the protocol and the usage instructions.

5.7. Overdose

An overdose is a deliberate or inadvertent administration of a product at a dose higher than specified in the protocol.

Overdose is not likely to occur in this study. Limited quantities of the product will be supplied, and closely monitored by the site for each subject.

Overdose per se is not an AE. However, any clinical sequelae of an overdose should be reported as an AE (and serious adverse event (SAE), if appropriate). For reporting, follow the AE and SAE reporting instructions.

5.8. Rescue Therapy

No rescue therapy is required in this study.

 GlaxoSmithKline	Document Name	Clinical Study Protocol 204477		
	Type	Version	Document Identifier	Effective Date
	eldo_clinical_doc	5.0; Most-Recent; Effective; CURRENT	090032d580daa95e	10-Oct-2017 06:16:49
	Reason For Issue	Auto Issue		

5.9. Product Assignment

Prior to the start of the study, schools within matched pairs will be assigned to test and control group in accordance with the randomisation schedule generated by the Biostatistics Department, GSKCH, using validated internal software.

5.9.1 Randomisation

A unique screening number will identify each participant screened for study participation. At each school, screening numbers will be assigned in ascending numerical order as each participant's parent/LAR signs their consent form.

This study will follow cluster randomisation where in schools will be termed as clusters and then matched pairs will be formed on the basis of criteria defined in Section 6.1. As schools are determined to be fully eligible and matched pairs are formed, schools within the matched pairs will be randomised according to the randomisation schedule provided to the study centres. Each matched pair will be assigned a randomisation number in ascending numerical order as each matched pair is formed.

Once 60% of participants from any gender have been enrolled within a study group, recruitment into that gender will stop to ensure that there is a maximum 60% of either male or female. Remaining 40% of participants will be recruited from other gender.

The randomisation schedule will be provided by the Biostatistics Department, GSKCH.

5.9.2 Blinding

This is an open-label study; hence there will be no requirement for blinding of study personnel at site and sponsor/CRO.

The study centre will receive a randomisation schedule to be used by the centre for randomisation of matched-pair clusters. This schedule will have a randomisation number for a matched pair of clusters followed by the study group (test/control) for intervention within clusters.

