5.9.3 Code Breaks

Since the investigator is un-blinded to the treatment there will be no requirement of breaking the code in the study by/for investigator.

 GlaxoSmithKline	Document Name	Clinical Study Protocol 204477		
	Type	Version	Document Identifier	Effective Date
	eldo_clinical_doc	5.0; Most-Recent; Effective; CURRENT	090032d580daa95e	10-Oct-2017 06:16:49
	Reason For Issue	Auto Issue		

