9.2.2. Exclusion of Data from Analysis

Prior to database lock and breaking of the study blind, review listings will be defined and reviewed by the Biostatistician and Medical Director (or designee) to identify protocol violations and to determine their level of impact on efficacy analyses. Further details of these review listings will be provided in the statistical analysis plan (SAP) and review listing specification document. The review listings may include, but will not be necessarily limited to, the following:

- Violation of inclusion or exclusion criteria that are deemed to affect efficacy.
- Use of prohibited treatment (e.g. usage of immunosuppressive therapy *e.g.*, oral corticosteroids or chemotherapy during the course of study) or medication before or during the study, which is felt to affect the assessment of efficacy.

 GlaxoSmithKline	Document Name	Clinical Study Protocol 204477		
	Type	Version	Document Identifier	Effective Date
	eldo_clinical_doc	5.0; Most-Recent; Effective; CURRENT	090032d580daa95e	10-Oct-2017 06:16:49
	Reason For Issue	Auto Issue		

- Non-compliance with product administration.
- Comments.

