2.2 Final Analyses

The final planned primary analyses will be performed after the completion of the following sequential steps:

1. All participants who have completed the study as defined in the protocol.
2. All required database cleaning activities have been completed and database has been locked.

3. All criteria for un-blinding the randomization codes have been met and the randomization codes have been distributed.

3 Considerations for data analyses and Data Handling Conventions

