3.4 Time points and Visit Windows

The time points and visits for this study are defined in the section “Schedule of Events” of the protocol. Any deviation from the study schedule will be reviewed case-by-case basis to determine whether the data should be excluded from the Per Protocol (PP) population. A time window non-compliance listing will be produced for the Blinded Data Review Meeting (BDRM) only.

4 Data Analysis

Data analysis will be performed by Syneos Health. The statistical analysis software used will be SAS Studio version 9.4 or higher.

Prior to database closure a BDRM will be conducted in which various aspects of the trial will be discussed and agreed.

Unless otherwise described below, all listings will be produced for enrolled population.

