| Per-Protocol | 
 Participants who have all post-treatment assessment and do not have any major protocol deviations that would affect efficacy assessments. Participants with major protocol deviations will be excluded. Depending on the nature of the major protocol deviation and impact on the efficacy variable (s), subjects will be either completely excluded from PP population or only partially excluded from the PP analyses. This will be determined on a case-by-case basis. | 
 Efficacy |

The primary population for assessment of efficacy will be the mITT Population. A PP analysis will be performed on the primary variable if more than 5 % of the subjects in the mITT Population are excluded from the PP Population.

Participants excluded from any of the analysis populations will be listed ([Listing 16.2.3.1](#)), with the reason for exclusion.

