4.3.1 Study Product Compliance and Exposure

For doses administered at school, study-personnel will supervise and ensure complete consumption of test product.

The descriptive summary of total number of expected amount of product to be consumed, actual amount product consumed by product group and overall for all participants in mITT population (Table 14.2.1.1).

The compliance will be calculated using following formula –

Test product compliance:

Test product compliance = Actual Consumption X 100/Expected Consumption

Where, actual and expected consumption are defined below:

- Expected consumption = (2X 150 mL of drink X number of days* between first and last treatment day in the study)
- Actual consumption = Expected consumption – (xx mL total left over at morning + xx mL left over at evening)]

*up to maximum of 9 months (to be converted in days) (as test product is only administered maximum up to 9 month regardless last visit day in study)

Dietary Counselling Compliance:

The dietary counselling compliance will be calculated using following formulas:

- **Participants:**
 - Compliance with Mandatory dietary counselling= (Number of sessions out of session numbers 1 or 2 attended by participant divided by 2) X 100
 - Compliance with Follow-up sessions dietary counselling= (Number of sessions out of session numbers 3-7 attended by participant divided by 5) X 100
- **Parents/LAR:**
 - Compliance with Mandatory dietary counselling= (Number of sessions out of session numbers 1 or 2 attended by parents/LAR divided by 2) X 100
 - Compliance with Follow-up sessions dietary counselling= (Number of sessions out of session numbers 3-7 attended by parents/LAR divided by 5) X 100

Study product compliance listing ([Listing 16.2.5.1](#)) using enrolled population will be presented at the time of blinded data review process. Noncompliance will be assessed on a participant by participant basis. Those participants with product compliance less than 70% or non-compliant with dietary counselling will be excluded from the PP population. Any participant excluded from PP population will be clearly documented in the population definition document.

Exposure to the study product in days will be calculated as date of last day in the study minus date of first date of study product administration +1 for the test group.

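### Per-protocol exclusions are described as agreed in a blinded review, but the trial is open-label and no masking of arm or outcome is specified for that review

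*Protocol*

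**What the plan says.** **On blinding.** Protocol 5.9.2 declares the study open-label, "hence there will be no requirement for blinding of study personnel at site and sponsor/CRO". Protocol 5.9.3 dispenses with code breaks for the investigator: "Since the investigator is un-blinded to the treatment". Under Protocol 5.9, schools are assigned from a "randomisation schedule generated by the Biostatistics Department, GSKCH". SAP 3.3 gives four schools, two in each product group.

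**On the review.** Protocol 9.2.1 places the final decision on running a PP analysis before un-blinding. Protocol 9.2.2 says: "Prior to database lock and breaking of the study blind, review listings will be defined and reviewed by the Biostatistician and Medical Director" (or a designee). SAP 2.2 lists as a step before the final analysis: "All criteria for un-blinding the randomization codes have been met and the randomization codes have been distributed". SAP 3.4 produces a visit-window listing for a Blinded Data Review Meeting (BDRM) only, and SAP 4 adds: "Prior to database closure a BDRM will be conducted in which various aspects of the trial will be discussed and agreed". SAP 4.1.2 has deviations reviewed before un-blinding. SAP 4.2.2 sends a medical history listing to the blinded review stage. SAP 4.3.1 says that the compliance listing, 16.2.5.1, "using enrolled population will be presented at the time of blinded data review process".

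**On discretion.** SAP 4.1.3 lets a child with a major deviation be wholly or only partly excluded from PP: "This will be determined on a case-by-case basis". SAP 3.4 treats visit-window deviations in the same way. The list of major deviations in SAP 4.1.2 is expressly not exhaustive and ends with a residual category for anything else thought to affect efficacy.

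**The concern.** Agreeing exclusions blind protects a PP analysis because the people deciding cannot tell which arm a decision favours. An open-label trial cannot rely on that. Its usual substitute is to decide without seeing outcomes, and to fix the list of exclusions before outcomes are released to those deciding. These documents invoke the first protection, which the design does not supply, and do not write down the second.

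Two things are at stake. People who know the arm may choose which children leave the PP analysis of the primary variable. The study report may also describe those choices as blinded when they were not.

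**Working it through.** The main check is a comparison of passages. One small calculation shows where the PP trigger falls.

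**1. Who can know the arm?** Protocol 5.9.2 covers site, sponsor and CRO. The sponsor's own biostatistics group generates the school schedule (Protocol 5.9), and the reviewers named in 9.2.2 are a biostatistician and the medical director. With four schools allocated whole, anyone who knows a child's school and that school's allocation knows the arm.

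**2. Could the cited listing be masked?** The shell of Listing 16.2.5.1 prints the product group at the top and has columns for expected drink, drink consumed and test-product compliance. Control children receive no drink. Removing the header would still leave test children identifiable from the filled columns.

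**3. How much is judgement?**

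| Ground for PP exclusion | How decided | Source |
|---|---|---|
| Product compliance below 70% | Fixed rule | SAP 4.3.1, Protocol 5.5 |
| Counselling non-compliance | Fixed rule | SAP 4.3.1, Protocol 6.10 |
| Visit-window deviation | Case by case | SAP 3.4 |
| Full or partial exclusion for a major deviation | Case by case | SAP 4.1.3 |
| Residual category | Open | SAP 4.1.2 |

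SAP 4.3.1 also says that non-compliance is assessed child by child, which blurs its own fixed rules. The shell of Table 14.1.2 has a row for major deviations that do not lead to PP exclusion, so discretion is expected in practice.

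**4. What protection is written down?** The timing is: review comes before database lock. Neither document specifies a masked reviewer, dummy codes for arm or school, or the withholding of Diagnosis Form data. Those forms are completed weekly (Protocol 6.11.3 and 6.12), so illness data exist well before lock.

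**5. Which analyses are reached?** SAP 4.1.3 makes mITT the primary efficacy population and defines it as ITT children who attended up to the end-of-study visit. PP is run on the primary variable only if more than 5% of mITT is excluded from PP.

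- Planned completers: 215 × 1.5 = 322.5, rounded up to 323 per arm, and 2 × 323 = 646. This reproduces the plan.
- Trigger: 0.05 × 646 = 32.3, so the 33rd exclusion starts the PP analysis.

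This assumes that mITT equals the 646 planned completers. If the fixed rules bring the count close to 33, a few discretionary decisions settle whether the PP analysis is run at all, as well as who is in it.

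**The case against.** **Not requiring blinding is not forbidding it.** This is correct. SAP 2.2 also holds back distribution of the codes until after lock. A reader might infer that everyone involved necessarily knows the arm, and the documents do not say that. What they support is narrower: no masking is specified, and an unspecified safeguard cannot be relied on.

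**What the reviewers see is partly inferred.** Protocol 9.2.2 defers detail to the SAP and to a review listing specification document, which is not among the documents reviewed here. The shell of Listing 16.2.5.1 carries a different protocol number (207192), so it may be a carried-over template, and a masked version for the meeting could exist. However, SAP 4.3.1 names this listing for the review, and the drink columns are there by necessity.

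**No illness data are assigned to the meeting.** A reader might infer that the reviewers will have ill-day counts in front of them. The documents do not support that. The content named is eligibility, prohibited treatment, product non-compliance, comments, visit windows, medical history and compliance. The list in Protocol 9.2.2 is open-ended, though, and nothing rules illness data out.

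**Several controls already exist.** The 70% and counselling rules are fixed, the review precedes lock, and exclusions are documented and listed with reasons. This narrows the concern to the discretionary categories but does not remove it.

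**Conclusion.** The point holds within limits. The plan states that PP exclusions are agreed blind. The design does not provide that property, and neither document puts an outcome-masked review in its place. The effect is on the supportive PP analysis and on whether its 5% trigger is met.

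A stronger reading would be that the primary result is exposed. Protocol 9.2.2 speaks of efficacy analyses generally, Protocol 3.2 removes users of immunosuppressive therapy from them, and the rationale in SAP 5 mentions leaving out children found ineligible after enrolment. But the mITT definition in SAP 4.1.3 has no criterion that depends on a reviewer's judgement. It turns on attending the end-of-study visit, so the primary test is not directly affected.

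No bias in days can be given, because the documents say nothing about illness rates among children who might be excluded. The verdict assumes that no separate specification document already imposes masking. If one does, the remaining task is to cite it and correct the wording.

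**What to change.** Amend the SAP and, where it uses the same language, the Protocol:

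1. Delete the references to a study blind, un-blinding and blinded data review, and describe the meeting as a data review in an open-label trial.
2. State that PP exclusions are decided without Diagnosis Form data, absenteeism or any ill-day derivation.
3. Dummy-code arm and school in the listings for arm-neutral deviations: eligibility, prohibited medication and counselling attendance.
4. Apply the existing 70% product rule and the counselling rule by program, without discussion at the meeting. Product compliance cannot be masked, since only one arm has it.
5. Sign and lock the population list before the reviewers receive any illness data.

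The cost is SAP and Protocol wording and re-cut review listings. The one small downside is that reviewers cannot use a child's illness history when judging a deviation.
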